4.2.3 Administration of VRC07-523LS

All study product administrations will be completed according to the assigned group. For women of childbearing potential, product administration may not proceed unless a negative pregnancy test has been obtained within the previous 24 hours. Prior to each product administration, temperature, blood pressure, heart rate (pulse) and weight will be collected and a targeted physical examination (based on signs, reported symptoms or interim medical history) may be conducted. In all study groups, the subject will be observed for at least 4 hours following each product administration.

If a subject is assigned to an IV administration group, the IV access will be placed in an arm vein in an aseptic manner. A different site may be used for collection of PK blood samples; however, the same site may be used after flushing the line if another site is not available. VRC07-523LS will be administered with approximately 100 mL normal saline IV over about 30 minutes or longer. If the subject experiences side effects during the infusion, the rate of infusion may be slowed or stopped to alleviate the symptoms.

If a subject is assigned to a SC administration group, the SC administration site(s) to be used will be discussed with the subject and must be assessed as acceptable by the clinician and the subject. The preferred SC administration site is the abdomen, but the upper arm or thigh may be used. Given the weight criterion in this study, the maximum volume needed to administer a 5 mg/kg SC dose is not expected to exceed 5.75 mL. The SC dose will be administered by standard needle and syringe SC injection methods with about 2.5 mL per injection site. Up to 4 SC injection sites may be used if deemed necessary by the clinician. SC administration sites should be at least 2 inches apart.

Procedures for VRC07-523LS preparation and administration are described in Section 7.

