6.4.5 Pharmacokinetics Analysis

Blood samples for PK evaluations will be collected at timepoints per the Schedule of Evaluations.

Individual Subject Pharmacokinetic Analysis: A non-compartmental PK analysis will be performed using Phoenix (Centara) or a similar program on the VRC07-523LS concentration data generated from each subject. Calculated PK parameters for IV Groups 1, 2, 4, 5, and 7 will include: area-under-the-curve (AUC), maximum concentration (Cmax), time to Cmax (Tmax), clearance (CL), volume of distribution (Vdz), terminal elimination rate constant (λz) and the terminal half-life ($T_{1/2}$). For Groups 3 and 6, the PK parameters will include AUC, Cmax, Tmax, apparent clearance (CL/F), apparent volume of distribution (Vdz/F), λz and $T_{1/2}$. Cmax and Tmax will be taken directly from the observed concentration-time data. The terminal slope, λz , will be determined from the log-linear portion of the curve and the $T_{1/2}$ calculated as $0.693/\lambda z$. $AUC_{0-Clast}$ will be determined using the linear trapezoidal method, where C_{last} is the concentration at 12 weeks after the first two doses in Groups 6 and 7 and the concentration at 24 weeks after dose in Groups 1, 2, 4 and 5 and final dose in Groups 6 and 7. If the final sample (C_{last}) has measurable VRC07-523LS concentrations, the remaining AUC after the final concentration ($AUC_{Clast-inf}$) will be estimated as $Clast/\lambda z$. Data will be summarized based by each dose group and overall for IV administration

groups for CL, Vd and $T_{1/2}$. For Groups 6 and 7, potential accumulation will be assessed as the ratios of the $AUC_{0-\infty}$ and C_{max} for the first and the last doses. The potential for non-linearity PKs among IV groups will be determined by comparing the dose-adjusted ratios for C_{max} and AUC between IV groups. Additional compartmental analysis will be performed as warranted by the data.

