7.4.1 VRC-HIVMAB075-00-AB: Preparation for Administration Intravenously

For each IV infusion order, the subject's weight and dose level or randomization code will be included in the pharmacy order. To prepare an IV infusion, the pharmacist will calculate the total milligrams needed, retrieve the minimum number of thawed, particle free vials needed to prepare the full dose and add the calculated total mg needed to a 100 mL bag of normal saline using good pharmacy practices to maintain sterility. Prior to preparation for administration, vials should be gently swirled for 30 seconds avoiding foaming. DO NOT SHAKE THE VIAL. Typically, 50 to 100 mL of additional volume may be added to a 100 mL bag of normal saline. Each pharmacist should test the capacity of the brand of saline bags that will be used at the site to confirm the capacity to add additional volume.

An in-line filter infusion set must be used for IV product administrations. In-line filters must comply with the following specifications: 1.2 micron PES (polyethersulfone) filter membrane, DEHP-free, latex-free (equivalent to Braun #473994 filter extension set). When the in-line filter is added to the tubing, prime the administration set. Flush the administration set with about 30 mL or appropriate volume of normal saline at the end of product administration

The study product solution will typically be administered IV over about 15 to 30 minutes or more as needed using a volumetric pump. The total time needed to administer the dose may be longer based on factors such as subject tolerance. The rate of infusion may range from 10-20 mg/kg/hr with the lowest dose group to 80-160 mg/kg/hr with the highest dose group. The mL/hr infusion rate may vary based on the total volume needed to administer a full dose.

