³ The PK blood draw "visits," defined by hours after an infusion, are relative to the exact time of the end of infusion (EOI). The exact start and end times of product administration and the time of PK blood draw(s) are recorded to ensure accurate PK analysis. All subjects will be observed for 4 hours after each product administration.

⁴ ALT, AST, ALP and creatinine will be collected at all scheduled timepoints. Comprehensive metabolic panel (CMP) will be collected at screening, baseline, and 2 weeks after each product administration and as needed at additional timepoints.

⁵ Pregnancy test results must be negative for women of reproductive potential before each product administration. Complete a Reproductive Information Form when pregnancy test is given.

⁶ HLA type blood sample is collected once at any timepoint in the study and is shown as a Visit 11 evaluation for convenience; however, if HLA type is already available in the medical record it does not need to be repeated. HLA type may also be obtained from a frozen sample.

⁷ Oral mucosa sample collection is encouraged but not mandatory. Oral samples will not be collected for Group 1. [X] indicates optional, as needed.

Visit windows: Visits 02A, 02B and 02C (± 10 min); Visit 02D (-2 hrs), Visits 03, 04 (± 6 hrs); Visits 06, 07, 08, 09 (± 2 days), and Visits 10, 11, 15, 16 and 17 (± 7 days).

Visits 05, 12, 13 and 14 are not applicable to Schedule 1.

Schedule 2: Group 3 (5 mg/kg SC)																
Visit Number		01R	02	02A	03	04	05	06	07	08	09	10	11	15	16	17
Time After Infusion			Pre	EOI	24hr	48hr	72hr	Wk1	Wk2	Wk3	Wk4	Wk8	Wk12	Wk16	Wk20	Wk24
¹ Day of Study		-42 to -1	D0	D0	D1	D2	D3	D7	D14	D21	D28	D56	D84	D112	D140	D168
Clinical	Tube	Screen	Enroll	Day of injection												
VRC 500 Screening Consent		X														
VRC 605 AoU; Consent			X													
² Screen: Physical exam, ht, wt; Other: targeted exam, BP, pulse, temp; also wt at visit 02		X	X	X	X	X	X	X	X	X	X	X	X	X	X	X
Complete med history at screen; then interim med history		X	X	X		X	X	X	X	X	X	X	X	X	X	X
³ VRC07-523LS Administration				X												
Begin 3-day Diary Card				X												
CBC / differential	EDTA	3		3		3			3	3		3				
⁴ ALT, AST, ALP, creatinine (total bili, BUN, albumin, protein, calcium, Na, K, Cl, CO ₂ , glucose)	GLT	4		4		4			4	4		4				
Urine protein		X		X						X						
⁵ Pregnancy test: urine or serum		X	X	X						X			X		X	
⁵ Pregnancy prevention counseling/ Reproductive Information Form		X	X	X						X			X		X	

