⁶ Oral mucosa sample collection is encouraged but not mandatory. [X] indicates optional, as needed.

*Subjects who discontinue product administration may be followed weekly for 4 weeks, then monthly for 24 weeks after last administration, per Schedule 4 (continued).

Visit windows: Visits A, B, and C (± 10 min); Visit 02D (-2 hrs); Visit E (+1 day); Visits 03, and 04 (± 6 hrs); Visits 06, 07, 13, and 14 (± 2 days); Visit 12 (+2 days), Visits 09, 10, 11, 15, 16 and 17 (± 7 days, with not less than 21 days between infusions). Visits 05, 08, and 18 are not applicable to Schedule 4.

Schedule 4 (continued): Group 7 (20 mg/kg IV by repeat dosing)												
	Visit Number*	17E	18	19	20	21	22	23	24	25	26	27
	Time After Infusion	24hr	72hr	Wk25	Wk26	Wk27	Wk28	Wk32	Wk36	Wk40	Wk44	Wk48
	Day of Study	D169	D171	D175	D182	D189	D196	D224	D252	D280	D308	D336
Clinical	Tube											
Targeted physical exam, BP, pulse, temp			X	X	X	X	X	X	X	X	X	X
Complete med history at screen; then interim med hx			X	X	X	X	X	X	X	X	X	X
Phone contact; clinic visit if indicated			X									
CBC / diff	EDTA		3	3	3			3	3			
¹ ALT, AST, ALP, creatinine (total bili, BUN, albumin, protein, calcium, Na, K, Cl, CO ₂ , glucose)	GLT		4	4	4			4	4			
Urine protein						X						
Pregnancy test: urine or serum						X			X			X
² Pregnancy prevention counseling / Reproductive Information Form						X			X			X
HIV EIA (other tests, if needed)	SST			4								
HIV prevention counseling					X				X			
³ HLA type	EDTA				20							
Research Samples												
Timed PK samples	SST			4	4	4	4	4	4	4	4	4
⁴ Oral sample							[X]			[X]		[X]
PBMC and plasma	EDTA				20							
Serum	SST			16	16	16	16	16	16	16	16	16
Daily Volume (mL)		0	7	31	67	20	27	27	20	20	20	20
Cumulative Volume (mL)		460	467	498	565	585	612	639	659	679	699	719

¹ ALT, AST, ALP and creatinine will be collected at all scheduled timepoints. Comprehensive metabolic panel (CMP) will be collected at screening, baseline, and 2 weeks after each product administration and as needed at additional timepoints.

² Complete a Reproductive Information Form when pregnancy test is given.

³ HLA type blood sample is collected once at any timepoint in the study and is shown as a Visit 20 evaluation for convenience; however, if HLA type is already available in the medical record, it does not need to be repeated. HLA type may also be obtained from a frozen sample.

⁴ Oral mucosa sample collection is encouraged but not mandatory. [X] indicates optional, as needed.

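### The end-of-infusion PK window admits draws made before the dose is fully given, and same-line draws are allowed but not recorded; both reach observed Cmax, mostly in a small or unquantified way

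*Combined protocol and SAP*

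**What the plan says.** Section 4.2.3, on the draw site for IV subjects, allows PK samples to come from a different site and adds that "the same site may be used after flushing the line if another site is not available". The section gives no flush or discard volume for such a draw and does not ask for the site to be recorded.

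Appendix III sets the windows: "Visits 02A, 02B and 02C (± 10 min" in Schedule 1 (Groups 1, 2, 4 and 5) and "Visits A, B, and C (± 10 min" in Schedule 4 (Group 7). The footnotes to both schedules time these visits from the exact end of infusion, so the minus side of the EOI window falls during the infusion.

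Section 6.4.5: "Cmax and Tmax will be taken directly from the observed concentration-time data". Cmax then feeds the first-to-last-dose accumulation ratio in Groups 6 and 7 and the dose-adjusted comparison across IV groups.

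The two statements of infusion duration differ. Section 4.2.3 says "VRC07-523LS will be administered with approximately 100 mL normal saline IV over about 30 minutes or longer"; Section 7.4.1 says "The study product solution will typically be administered IV over about 15 to 30 minutes", or more as needed.

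**The concern.** An observed maximum has no model behind it to absorb a mistimed or contaminated sample. A draw before the end of infusion misses the peak, yet it is not a deviation and no rule in Section 6.4.5 treats it differently. A sample carrying traces of infusate reads high, and a maximum keeps a high error: a clean 1 h sample cannot displace it. Recorded times identify an early draw, but nothing identifies a same-line draw.

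At stake are the reported Cmax and Tmax in the five IV groups, the Group 7 accumulation ratio and the dose-proportionality comparison. Groups 1, 2, 4 and 5 have three subjects each and Group 7 has five, so one affected subject shows in a group mean. Section 6.4.6 also allows preliminary PK results to inform dose levels in other studies.

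**Working it through.** **1. The plan's own rates.** Section 7.4.1 gives 80-160 mg/kg/hr for the highest dose group. Rate = dose / duration: 40/0.5 h = 80 and 40/0.25 h = 160, so the figure reproduces with 15-30 minutes. The 10-20 mg/kg/hr given for the lowest dose group does not: 1 mg/kg over 15-30 minutes is 2-4 mg/kg/hr, while 5 mg/kg gives 10-20. Taken literally for 1 mg/kg, 10-20 mg/kg/hr means a 3-6 minute infusion, and EOI -10 min would precede its start.

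**2. Dose outstanding at EOI -10 min.** At constant rate over T minutes this is 10/T: 10/15 = 67%, 10/30 = 33%, 10/60 = 17%.

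**3. Effect on Cmax.** The documents give no human PK for this antibody, so this step uses a two-compartment infusion model under assumptions:

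- dA1/dt = R - (CL+Q)A1/V1 + Q·A2/V2
- dA2/dt = Q·A1/V1 - Q·A2/V2
- concentration = A1/V1

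CL is 0.016 L/h, the VRC01 value in Section 1.1. V1, V2 and Q are assumed. The dose is 20 mg/kg × 70 kg = 1400 mg over 30 minutes, with no drug present beforehand. Percentages are relative to the true peak.

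| V1, V2 (L), Q (L/h) | True peak (mcg/mL) | EOI -10 min | 1 h | 1 h +10 min | EOI +10 min |
|---|---|---|---|---|---|
| 3, 3, 0.02 | 465 | -33.3% | -1.2% | -1.4% | -0.2% |
| 3, 4, 0.05 | 464 | -33.2% | -2.2% | -2.5% | -0.4% |
| 2.5, 5, 0.15 | 551 | -33.0% | -6.3% | -7.3% | -1.1% |

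With a 15-minute infusion the EOI -10 min column becomes about -67%; the other percentage columns do not change. In every row the 1 h sample exceeds the early EOI sample, so it becomes Cmax. The error is 1.2% to 6.3%, or up to 7.3% if the 1 h draw is 10 minutes late.

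**4. When the 1 h sample is missing.** After the first IV dose, the 3 h and 6 h samples still cover Cmax. After Group 7 doses 2 and 3 they do not exist. Around dose 3 in Schedule 4, cumulative blood volume rises by 4 mL at each of two post-dose draws (452 to 456 to 460). It does not rise at the 24 h phone contact. It rises by 7 mL at 72 h (3 mL CBC + 4 mL chemistry, so no PK tube) and by 31 mL at Week 25, which includes PK. Cmax would then be the larger of the early EOI value and a value a week later.

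**5. Potential for carry-over.** Assumptions: plasma volume 43 mL/kg and body weight 50-115 kg (115 kg is the exclusion limit; 50 kg is assumed). The 103 mL bag and 100 mg/mL product are from Section 7.1.

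- Infusate = mg/(103 + mg/100); expected peak = mg/(43 × kg).
- 40 mg/kg, 50 kg: 2000/123 = 16.3 mg/mL against 2000/2150 = 0.93 mg/mL, ratio 17.5.
- 1 mg/kg, 115 kg: 115/104.15 = 1.10 mg/mL against 115/4945 = 0.0233 mg/mL, ratio 47.5.

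If a fraction f of the sample were undiluted infusate, inflation = f × (ratio - 1). For f = 1% this is 16.5% to 46.5%; for f = 0.1% it is 1.6% to 4.6%. Neither value of f comes from the documents.

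**The case against.** Much of the case against is right.

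- A reader might infer that reported Cmax could be 33% to 67% too low. The documents do not support that: the shortfall belongs to the EOI sample, and every IV dose has a 1 h sample that replaces it as the maximum.
- A reader might infer that Cmax is in practice inflated by carry-over. The documents make same-site drawing a fallback, only after flushing, and Section 7.4.1 adds a flush of about 30 mL at the end of administration. The ratios above concern undiluted infusate; they show potential, not an expected bias.
- The two problems largely exclude each other in one sample, because a draw after flushing the line does not fit with drug still running through it.
- Actual times are recorded (Section 4.2.5 and the schedule footnotes), so early draws can be found and the population model can use them. This does not correct an observed Cmax.
- Distortion of dose-proportionality would be modest. At 70 kg the ratios are 29.0 (1 mg/kg) and 23.0 (40 mg/kg). With 1% carry-over in every subject, the dose-adjusted comparison shifts by 1.28/1.22, about 5%. In Group 7, equal carry-over at first and last dose would largely cancel.
- Excluding same-line samples outright would do harm. After Group 7's third dose it could leave Week 25 as the first usable value.
- PK is a secondary objective in a study that calls itself mainly descriptive. Primary safety, escalation and pause rules do not use Cmax.

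What remains is that an avoidable early draw counts as in window, and that a same-line draw cannot be traced.

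**Conclusion.** The point holds as a cheap improvement, not as a threat to the study. The two-sided EOI window can lower observed Cmax by about 1% to 7% and move Tmax to the 1 h sample. Those figures rest on assumed V1 of 2.5-3 L, V2 of 3-5 L, Q of 0.02-0.15 L/h and a clearance borrowed from VRC01. A large error needs both an early EOI draw and a missing 1 h sample, and Group 7 doses 2 and 3 are where nothing else covers it. Carry-over is a possible upward bias of unknown frequency and size. The infusate is roughly 17 to 48 times the expected peak under the stated assumptions, and the plan as written could not tell which samples were exposed.

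**What to change.** 1. **Schedules 1 and 4:** set the window for EOI samples (02A, 11A, 17A) to 0 to +10 minutes after the recorded end of infusion. Leave time zero unchanged.
2. **Section 4.2.3:** state that a separate site is preferred for the EOI and 1 h PK samples, and record the draw site for each.
3. **Section 6.4.5:** keep all samples in the main analysis. Add a sensitivity analysis of Cmax, Tmax, the Group 7 accumulation ratio and dose-adjusted Cmax without same-line EOI and 1 h samples. Where this removes both same-day samples after Group 7 dose 2 or 3, report Cmax as not evaluable in that analysis rather than substituting the value a week later.
4. **Sections 4.2.3 and 7.4.1:** reconcile the two infusion durations, and the lowest-dose infusion rate with the 1 mg/kg group.

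The cost is wording changes, one database field and a small extra analysis. A draw at +10 minutes reads about 0.2% to 1.1% below the true peak in the scenarios above, against 33% or 67% for a draw at -10 minutes.

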4.2.4 Solicited Adverse Events and Clinical Follow-up

Subjects will be asked to record temperature and systemic symptoms daily for 3 days after each product administration. Subjects will be trained and encouraged to use the electronic database to record reactogenicity but will have the option to use the paper diary card. When the 3-day diary

card parameters are recorded directly by the subject into the database, the subject's electronic record will be available to clinicians in real time, and will be the source for these data. If concerns arise based on the electronic data, or if a subject uses a paper diary card, clinicians may follow up with additional phone calls during reactogenicity period as needed. The paper diary may be the source document, if used by the subject. When neither a written nor electronic diary is available from the subject, the clinician will note the source of reactogenicity information recorded in the study database.

For this study, solicited systemic parameters occurring during the 3 days after receipt of study product will include: unusually tired/feeling unwell, muscles aches, headache, chills, nausea and joint pain. Subjects will also record highest measured temperature daily. Subject diaries are reviewed for accuracy and completeness at follow-up visits and reactogenicity is recorded without an attribution assessment. Clinicians will follow and collect resolution information for any reactogenicity symptoms that are not resolved within 3 days.

Local symptoms will be assessed and recorded by the clinicians. Local reactogenicity parameters will include pain/tenderness, swelling, redness, bruising, and pruritus (itchiness) at the product administration site. Clinicians will assess the product administration site(s) for local reactogenicity on the day of product administration and during the scheduled follow-up timepoints for all groups.

Events that may require a clinic visit include rash, urticaria, fever of 38.6°C (Grade 2) or higher lasting greater than 24 hours or significant impairment in the activities of daily living (such as those consistent with Grade 2 or higher impairment). Additionally, arthralgia or other clinical concerns may prompt a study visit based on the judgment of a study clinician.

Clinical laboratory assays and clinical evaluations will assess safety and tolerability at specified intervals after each administration. Throughout the study, clinicians will also assess subjects for any changes in symptoms to include vision changes. Any new or concerning symptoms will be fully assessed to include specialty consultation at the NIH Clinical Center as indicated clinically.

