1.3.2 VRC01LS Safety Data

VRC01LS began evaluation in HIV-uninfected adults in the VRC 606 study in November 2015. Evaluation of VRC01LS in HIV-infected adults in the VRC 607 study was initiated in April 2017. There have been no SAEs reported in VRC 606 as of July 17, 2017. Overall 29 of 39 (74.4%) subjects who began product administrations have had one or more unsolicited AEs, with a maximum severity being Grade 1 for 18 subjects and Grade 2 for 11 subjects.

VRC01LS administrations have been generally well tolerated. Overall, 3 of 21 subjects (14.3%) who received VRC01LS IV and 14 of 18 subjects (77.8%) who received VRC01LS SC reported solicited local reactions in the week after product administration. The most frequent local reaction was pain/tenderness at injection site reported by 14 subjects (2 for IV and 12 for SC administration) at a maximum severity being mild, and being moderate by 1 subject for SC product administration. Other local reactogenicity symptoms included mild bruising (n=1), swelling (n=2), and redness (n=2).

With regard to solicited systemic adverse events, 13 of 39 subjects (33.3 %) had one or more mild systemic signs or symptoms reported in the 3 days after product administration. This included mild malaise (n=10), myalgia (n=6), headache (n=4), and nausea (n=4).

Observations during product administration included brief reactions of local pain and/or stinging sensations at SC administration sites (15 of 18 subjects, 83.3%) that resolved within 2-5 minutes after injection. These reactions were consistent with known risks of injections and did not meet criteria for reporting as AEs as defined by the Table for Grading Severity of Adverse Events. No systemic symptoms were reported during product administration.

As of 7/17/2017, no local or systemic reactogenicity were reported during VRC01LS administrations in VRC 607 study in HIV-infected adults; all infusions were completed as per protocol. All 4 subjects reported maximal solicited local reactogenicity as “none” on a 3-day diary card. As to systemic solicited reactogenicity, one subject reported mild symptoms of headache, chills, and nausea that resolved within 7-11 days after product administration. No SAEs were reported; all unsolicited AEs were Grade 1 (mild) or Grade 2 (moderate), and assessed as unrelated to study product.

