3. STUDY OBJECTIVES

3.1 PRIMARY OBJECTIVES

- To evaluate the safety and tolerability of VRC-HIVMAB075-00-AB administered as a single dose at 1 mg/kg IV, 5 mg/kg IV, 20 mg/kg IV, 40 mg/kg IV, and 5 mg/kg SC to healthy adults.
- To evaluate the safety and tolerability of VRC-HIVMAB075-00-AB administered at 20 mg/kg IV by repeat dosing every 12 weeks for a total of 3 infusions to healthy adults.
- To evaluate the safety and tolerability of VRC-HIVMAB075-00-AB administered at 5 mg/kg SC by repeat dosing every 12 weeks for a total of 3 injections to healthy adults.

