6.4.4 Tolerability Evaluation

The tolerability of the medical product represents the degree to which overt adverse effects can be tolerated by the subject [19]. VRC 605 is the first trial of VRC07-523LS in healthy adults. The tolerability evaluation will be mostly descriptive by nature and consist of solicited AEs that occur during the 3 days following each VRC07-523LS administration and reasons for any withdrawal or discontinuation based upon subject discomfort. This early assessment of tolerability of VRC07-523LS will inform which parameters should be solicited or routinely assessed to further characterize the tolerability profile in a larger number of subjects.

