Visit windows: Visit 02A (\pm 10 min); Visits 03, 04, 05 (\pm 6 hrs); Visits 06, 07, 08, 09 (\pm 2 days); Visits 10, 11, 15, 16, 17 (\pm 7 days). Visits 12-14 are not applicable to Schedule 2.

Schedule 3: Group 6 (5 mg/kg SC by repeat dosing)																							
Visit Number			01R	02	02A	03	04	05	06	07	09	10	11	11A	11E	12	13	14	15	16	17	17A	17E
Time After Infusion				Pre D0	EOI D0	24hr	48h	72hr	1wk	Wk2	Wk4	Wk8	Pre Wk12	EOI Wk12	24hr	72hr	Wk13	Wk14	Wk16	Wk20	Pre Wk24	EOI Wk24	24hr
1 ^{Day of Study}			-42 to -1	D0	D0	D1	D2	D3	D7	D14	D28	D56	D84	D84	D85	D87	D91	D98	D112	D140	D168	D168	D169
Clinical	Tube	Screen	Enroll		Day of injection									Day of injection							Day of injection		
VRC 500 Screening Consent		X																					
VRC 605 AoU; Consent			X																				
² Screen: Physical exam, ht, wt; Other: targeted exam, BP, pulse, temp; wt at visits 02, 11, and 17		X	X	X	X	X	X	X	X	X	X	X	X	X	X	X	X	X	X	X	X		
Complete med history at screen; then interim med hx		X	X	X		X	X	X	X	X	X	X	X			X	X	X	X	X			
³ VRC07-523LS Administration				X										X						X			
Begin 3-day Diary Card				X										X						X			
Phone contact; clinic visit if indicated															X							X	
CBC / diff	EDTA	3		3		3		3	3		3	3				3	3	3		3	3		
⁴ ALT, AST, ALP, creatinine (total bili, BUN, albumin, protein, calcium, Na, K, Cl, CO2, glucose)	GLT	4		4		4		4	4		4	4				4	4	4		4	4		
Urine protein		X		X						X				X					X		X		
⁵ Pregnancy test: urine or serum		X	X	X					X			X				X		X		X			
⁵ Pregnancy prevention counseling/ Reproductive Information Form		X	X	X					X			X				X		X		X			
HIV EIA (other tests, if needed)	SST	4					4									4							
HIV prevention counseling		X		X				X				X			X					X			
Research Samples																							
Timed PK samples	SST			4		4	4	4	4	4	4	4	4			4	4	4	4	4	4		
⁶ Oral sample			[X]											[X]						[X]			
PBMC and plasma	EDTA	20	20																				
Serum	SST	24	24	16		16	16	16	16	16	16	16	16				16	16	16	16	16		
Daily Volume (mL)		55	44	27	0	11	20	24	27	27	20	27	27	0	0	15	27	27	20	27	27	0	
Cumulative Volume (mL)		55	99	126	126	137	157	181	208	235	255	282	309	309	309	324	351	378	398	425	452	452	

¹ Day 0=day of first product administration. Day 0 is preferably scheduled within 14 days after enrollment, but may be scheduled up to 42 days after enrollment to allow for the possibility of study pauses or scheduling difficulty with the approval of the PI. Day 0 evaluations prior to product administration are the baseline for assessing subsequent AEs.

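### Local reactions in Groups 6 and 7 are looked for less often after doses 2 and 3 than after dose 1, so their ascertainment differs by dose

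*Combined protocol and SAP*

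**What the plan says.** Two of the three primary objectives in Section 3.1 concern repeat dosing. Group 6 receives 5 mg/kg SC "by repeat dosing every 12 weeks for a total of 3 injections to healthy adults", and Group 7 receives 20 mg/kg IV on the same calendar. Each group has 5 subjects.

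Section 4.2.4 splits solicited events by who records them. For systemic events, "Subjects will be asked to record temperature and systemic symptoms daily for 3 days after each product administration". For pain/tenderness, swelling, redness, bruising and pruritus, "Local symptoms will be assessed and recorded by the clinicians", and the clinicians look "on the day of product administration and during the scheduled follow-up timepoints for all groups". Section 4.2.3 requires at least 4 h of observation after every dose.

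Section 6.4.4 says the tolerability evaluation will "consist of solicited AEs that occur during the 3 days following each VRC07-523LS administration", together with withdrawals for discomfort. Section 6.4.3 counts each subject once per sign, at maximum severity over all assessments.

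In Appendix III, Schedules 3 and 4 give clinic visits at 24 h and 48 h after dose 1, and Group 6 also has one at 72 h. After doses 2 and 3 the 24 h entry (Visits 11E and 17E) is "Phone contact; clinic visit if indicated". No 48 h visit is listed, and the next clinic visit is Visit 12 or 18 at 72 h.

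**The concern.** The diary runs for 3 days after each dose but carries no local items, so the record of local reactions depends on when a clinician looks or asks. That schedule thins after dose 1. A by-dose display could then show fewer local reactions after doses 2 and 3 because fewer looks were made, and a real increase with repeated exposure could be partly hidden. The SC route is where this matters most. In Section 1.3.2 the related antibody gave local reactions mainly by that route: "14 of 18 subjects (77.8%) who received VRC01LS SC reported solicited local reactions in the week after product administration", against 3 of 21 by IV. Section 6.4.4 also intends these data to guide which parameters later trials solicit.

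**Working it through.** **Step 1: which contacts are clinic visits.** Check marks in the extracted schedules are partly displaced, so visit type was read from the blood-volume rows, whose running sums agree in the main tables of Schedules 3 and 4. In both groups the 24 h and 48 h visits after dose 1 carry 11 and 20 mL. Visits 11E and 17E carry 0 mL, which fits a phone contact. The 72 h visits after doses 2 and 3 carry 15 mL in Group 6 and 7 mL in Group 7.

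**Step 2: clinic days within 3 days of dosing, counting the dosing day.**

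| Group | Dose 1 | Doses 2 and 3 |
|---|---|---|
| 6 | D0, D1, D2, D3 = 4 | D0, D3 = 2, plus 24 h call |
| 7 | D0, D1, D2 = 3 | D0, D3 = 2, plus 24 h call |

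In Group 7, Visits 12 and 18 have a +2 day window: 72 h + 48 h = 120 h, or day 5. A visit that late falls outside the 3-day window of Section 6.4.4 and leaves one clinic day inside it.

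**Step 3: window and footnote conflicts.** Visit E is ±1 day in Schedule 3 but +1 day in Schedule 4. For a 24 h contact, ±1 day spans 0 to 48 h, so a Group 6 call on the dosing day complies. The Schedule 4 footnote says "Visits 05, 08, and 18 are not applicable to Schedule 4", yet Schedule 4 (continued) lists Visit 18 at 72 h with 7 mL of blood and its own window. If the footnote were followed, the next clinic look after dose 3 in Group 7 would be Visit 19, D175 − D168 = day 7.

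**Step 4: how much could be missed.** The documents give no onset or duration data for local reactions to this product, so this is an illustration on assumed inputs. Onset is uniform over 0 to L hours and duration is exponential with median m. A reaction counts if it starts within 4 h or is present at a look, and there is no recall. Looks are at 24, 48, (72) and 168 h after dose 1, and at 72 and 168 h after doses 2 and 3, with or without an eliciting call at 24 h.

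For L = 24 h and m = 24 h the answer has a closed form, with mean duration τ = 24/ln 2 and τ/24 = 1.4427:

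- Dose 1: 4/24 + 1.4427 × (1 − 2^(−20/24)) = 0.167 + 1.4427 × 0.439 = 0.80.
- Doses 2 and 3, clinic looks only: 4/24 + 1.4427 × (2^(−48/24) − 2^(−68/24)) = 0.167 + 1.4427 × (0.250 − 0.140) = 0.33.

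Simulation of 400,000 reactions agrees and extends this:

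| Onset; median duration | Dose 1 | Doses 2–3, clinic only | Doses 2–3, call elicits | 72 h visit slips to 120 h, no call |
|---|---|---|---|---|
| 0–4 h; any | 1.00 | 1.00 | 1.00 | 1.00 |
| 0–12 h; 6 h | 0.44 | 0.33 | 0.44 | 0.33 |
| 0–24 h; 24 h | 0.80 | 0.33 | 0.80 | 0.21 |
| 0–48 h; 12 h | 0.60 | 0.17 | 0.40 | 0.09 |
| 0–48 h; 24 h | 0.76 | 0.34 | 0.58 | 0.15 |

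The last column applies to Group 7 only. Over onset spreads of 12 to 48 h and median durations of 6 to 72 h, the clinic-only loss runs from 0.44 − 0.33 = 11 to 0.80 − 0.33 = 47 percentage points. With an eliciting call it runs from 0 to 0.60 − 0.40 = 20 points.

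**The case against.** A reader might infer that subjects have no scheduled way to report a local reaction on days 1 and 2 after doses 2 and 3, and that repeat-dose tolerability is therefore under-counted. The documents do not support that.

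- The 24 h call is a scheduled timepoint, and Section 4.2.4 places local assessment at scheduled timepoints. Pain and itch can be elicited by phone. If all onsets fall by 24 h, a call at 24 h that asks about the site closes the modelled gap completely, because anything present at 48 or 72 h was already present at 24 h.
- Interim history at the 72 h and later visits allows recall, and Section 5.1 collects all AEs for 56 days after each dose.
- In Group 7 the 72 h visit exists only after doses 2 and 3, so the net loss is one clinic day.
- No contrast of dose 1 with doses 2 and 3 is planned. A missed reaction changes the Section 6.4.3 table only if it would have been that subject's first, or most severe, instance of the sign. With 5 subjects, 3/5 (0.147 to 0.947) and 1/5 (0.005 to 0.716) in Table 5 overlap widely.
- Multiplying 77.8% by a detection probability to forecast counts would be wrong, because that figure is already a recorded rate.

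All of this limits the size of the problem, but it does not make the looks equal. Nothing says the call asks about the site. The events listed in Section 4.2.4 as possible reasons for a clinic visit (rash, urticaria, fever, significant impairment) would not ordinarily capture a mild local reaction, which is left to clinician judgment. Appendix IV grades solicited bruising by largest diameter, which a call cannot inspect.

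**Conclusion.** The point holds as unequal ascertainment of local reactions by dose in Groups 6 and 7, with a risk of missing transient or size-graded reactions after doses 2 and 3. The clinic-day counts (4 to 2, and 3 to 2) come directly from the schedules. The resulting loss is unknown: none if onset falls within the 4 h observation, or if onset is by 24 h and the call elicits local symptoms at that time; up to about 47 percentage points on the assumed grid if the call elicits nothing, and more where the Group 7 visit slips to day 5. A statement that events are in fact under-counted, or that repeat-dose tolerability as a whole is compromised, would go too far: the systemic diary covers 3 days after every dose. The Visit 18 contradiction is a separate, plain inconsistency in the schedule.

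**What to change.** - In Section 4.2.4 and the diary, add the five local parameters already named there to the 3-day diary after every dose. Keep clinician inspection as confirmation. Section 1.3.2 describes a 3-day diary card that captured local reactogenicity in the related study VRC 607, so there is a precedent.
- State that the 24 h phone contact asks about the same five parameters.
- In Section 6.4.4, require that any by-dose display of local reactogenicity show its look schedule and flag subjects dosed before the diary change. Section 1.3.3 shows that dosing had already begun.
- Reconcile the Schedule 4 footnote on Visit 18 with Schedule 4 (continued) and its Visit 18 window.
- Reconcile the Visit E windows of Schedules 3 and 4.

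The cost is five more items in a diary already in use and some text edits, with no added visits. The downsides are slightly more subject burden, subject-reported rather than clinician-measured sizes on days without a visit, and a difference in ascertainment between subjects dosed before and after the change, which is why the flag is needed.
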